1 LIST OF ABBREVIATIONS

Abbreviation	Definition
ACLD	acute on chronic liver disease
AE	adverse event
ALFSG	Acute Liver Failure Study Group
ALF	acute liver failure
ALI	acute liver injury
ALT	alanine aminotransferase (= serum glutamic pyruvic transaminase, SGPT)
ANA	antinuclear antibody
ASMA	anti-smooth muscle AB
AST	aspartate aminotransferase (= serum glutamic oxaloacetic transaminase, SGOT)
ATN	acute renal tubular necrosis
AUC	area under the concentration–time curve
AUC _{0-last}	area under the concentration–time curve from the time of dosing (Time 0) to the time of the last measureable concentration
CAH	chronic autoimmune hepatitis
C _{max}	observed maximum concentration
CMV	cytomegalovirus
Cr	creatinine
CRF	case report form
CTCAE	Common Terminology Criteria for Adverse Events
CVVH	continuous veno-venous hemofiltration
dL	Deciliter
EBV	Epstein-Barr virus
ECG	Electrocardiogram
EDTA	edetic acid (ethylenediaminetetraacetic acid)
FDA	Food and Drug Administration
g	grams
GCP	Good Clinical Practice
h/hrs	hour/hours

Abbreviation	Definition
HAV	Hepatitis A virus
HBc	Hepatitis B core
HBsAg	Hepatitis B surface antigen
HDV	Hepatitis delta virus
HE	hepatic encephalopathy
Hg	mercury
HSV	Herpes simplex virus
ICF	Informed consent form
ICH	International Conference on Harmonization
ICP	intracranial pressure
IgG	Immunoglobulin G
IgM	Immunoglobulin M (antibody)
ICU	Intensive Care Unit
IND	Investigational new drug
IMM	Internal Medical Monitor
INR	International Normalized Ratio (for prothrombin time)
IRB	Institutional Review Board
IU/L	international unit per liter
IV	Intravenous
K3+EDTA	tri-potassium edetic acid (ethylenediaminetetraacetic acid)
LAR	legally authorized representative
LKMA	anti-liver-kidney microsome antibody
µL	Microliter
µmol/L	micromole per liter
MedDRA	Medical Dictionary for Regulatory Activities
mg	milligram
mL	milliliter
mm	millimeter

Abbreviation	Definition
msec	millisecond
MSM	Medical Safety Monitor
MOO	Manual of Operations
NAC	N -acetylcysteine
ng	nasogastric
OCR-002	ornithine phenylacetate
O-log	Orientation Log
PAGN	Phenylacetylglutamine
PCR	polymerase chain reaction (viral diagnostic test)
PD	Pharmacodynamic
PK	Pharmacokinetic
Qt Interval	time from electrocardiogram Q wave to the end of the T wave corresponding to electrical systole
RNA	ribonucleic acid
SAE	serious adverse event
SAR	suspect Adverse Reaction
SDCC	Statistical and Data Coordinating Center
SOP	standard operating procedure
SRC	Safety Review Committee
T0	Treatment Day 1 - Time “0”
T1/2	half-life
ULN	upper limit normal
US	United States
X	Times

2 PROTOCOL SYNOPSIS

Protocol Number/Title	ALFSG-OCR-002: A Phase 2a Study to Evaluate the Safety and Tolerability of OCR-002 (ornithine phenylacetate) in the Treatment of Patients with Acute Liver Failure/Severe Acute Liver Injury (STOP-ALF)
Phase	Phase 2a
Objectives	
Primary Objectives:
 
To evaluate the safety and tolerability of OCR-002 in patients with acute liver failure/severe acute liver injury
 
Secondary Objectives:
 
To evaluate the steady state pharmacokinetic and pharmacodynamic profile of OCR-002 in patients with minimal renal dysfunction using urinary PAGN as a surrogate marker
 
To evaluate the effect of OCR-002 on ammonia levels in patients with acute liver failure/severe acute liver injury
 
To evaluate the effect of OCR-002 on neurological function in patients with acute liver failure/severe acute liver injury

Study Chair	[name], UT Southwestern Medical Center, Dallas, TX
Co-Principal Investigators	[name], University of Michigan, Ann Arbor, MI R. [name], VCU Medical Center, Richmond, VA
Investigative Sites	Approximately 6-12 investigative sites in the United States
Study Design	
This is a Phase 2a, multi-center, open-label study, conducted in two cohorts of patients diagnosed with acute liver failure/severe acute liver injury (ALF/ALI) who meet inclusion/exclusion criteria. Cohort 1 is defined as patients with ALF/ALI with minimal renal dysfunction at the time of enrollment (defined as a serum creatinine ≤ 1.5 mg/dL and mean arterial pressure of >65 mm Hg). Cohort 2 is defined as patients with ALF/ALI with compromised renal function (defined as a serum creatinine >1.5 mg/dL and <10 mg/dL with mean arterial pressure of >65 mm Hg).
 
Informed consent will be obtained from the patient and/or patient's legally authorized representative (LAR) or family member as defined in 21CFR50.3(m). All patients will receive medical care for acute liver failure/severe acute liver injury according to the institution's standards of care. Standard of care may include, but is not limited to, administration of N-acetylcysteine and consideration for orthotopic liver transplantation.
 
Up to 36 evaluable patients will be enrolled. An evaluable patient is one who has received an infusion of OCR-002 for at least 72 hours. It is expected that not every enrolled patient will be treated for at least 72 hours due to transplant, death or early hospital discharge. Due to this, we anticipate 25% of the enrolled population will fail to reach evaluable status. Therefore, we plan to enroll up to 50 patients in order

Study Design Continued	
to obtain 36 evaluable patients. Dosing with OCR-002 may be initiated immediately after obtaining signed informed consent; or, up to 32 h after obtaining consent should the time be necessary to complete any pre-study drug initiation requirements and/or to provide a time frame for study drug administration.
 
Baseline is immediately prior to the start of the initial infusion. At Treatment Day 1 - Time “0” (T0) and after baseline measurements, patients enrolled at Dose Levels 1 through 3 will receive an initial infusion rate of OCR-002. Dose will be escalated to a maximum dose of 10g/24h infusion as indicated herein. Patients receiving Dose Level 4 will receive the full 20 gm/24 hour dose level from initiation of infusion for a maximum time of 120 hours with no further dose escalation, provided the dose level is well tolerated with no noteworthy side effects. Titration of dose will depend on evidence of safety and tolerability (refer to Treatment section below).
 
Patients may have an IV catheter inserted as a safer and easier method for obtaining repeated blood sampling and a separate IV for the infusion. Blood samples for measurement of plasma ornithine, phenylacetate and PAGN concentrations will be collected at multiple time-points during the infusion period, at the Completion of the Last Infusion and up to 24 hours Following the Completion of the Last Infusion. Urine will be collected at specific intervals to determine the amount of PAGN excreted.
 
Patients will be assessed for safety and tolerability of OCR-002 as well as pharmacokinetic and pharmacodynamic variables during the infusion period, at the Completion of the Last Infusion and 24 hours Following the Completion of the Last Infusion. Data on clinical outcomes will also be collected during the study period.
 
Safety data will be reviewed by a Safety Review Committee (SRC) operating under an approved charter and made up of three ALFSG clinicians who are independent of the participating clinical sites and a clinical pharmacologist with experience in PK and clinical trials. Throughout the trial, the SRC will review all safety data at regular intervals, and the FDA will receive annual IND reports.
 
Supportive Care
 
Inotropic support may be used to maintain mean arterial pressure above 65 mm Hg in patients who are hypotensive either before or after enrollment. Dialysis or continuous veno-venous hemofiltration (CVVH), endotracheal intubation and mechanical ventilation will be considered as indicated. Cerebral edema will be managed post-enrollment with mannitol or hypertonic saline per local institutional practices. Antibiotic therapy may be initiated and modified as required. In patients who have intracranial pressure (ICP) monitors placed, ICP, cerebral perfusion pressure and mean arterial pressure will be recorded continuously and reported hourly.

Study Drug	OCR-002 (ornithine phenylacetate) Supplied to the Investigator by Ocera Therapeutics, Inc., Durham, NC
Treatment	Patients enrolled in Dose Levels 1 through 3 will receive an initial infusion at the lowest dose level. The infusion will be escalated in two dosing levels, provided the previous dose level is well-tolerated with no noteworthy side effects. If a patient

Treatment Continued	
experiences CTCAE grade 1 or 2 adverse reactions or intolerance to the assigned dose, the investigator may choose to titrate back to the lower tolerated dose and closely monitor the patient. The infusion rate and dose may be discontinued if the patient experiences CTCAE grade 3 or higher, or any time at the investigator's discretion. Each dose level between 1 and 3 will be administered to Cohort 1 patients and safety and PK data reviewed, prior to exposing Cohort 2 patients to the study drug and subsequent dosing levels. Dose level 4 will be administered to both Cohort 1 and 2 beginning simultaneously.
 
The dosing levels for Dose Levels 1 through 3 are defined follows:
 
Dose Level 1:
 
Patients will receive the initial infusion of study drug at 0.139 g/h for the first 12 hours (approximately 3.33 g/24h or 6.9 mL/h) and be maintained at this rate for up to 5 days.
 
Dose Level 2:
 
For patients assigned to this dose level, the infusion will be initiated at 0.139 g/h for the first 12 hours (approximately 3.33 g/24h) and increased to 0.277 g/h (approximately 6.65 g/24h or 13.8 mL/h) for the remainder of the treatment period.
 
Dose Level 3:
 
For patients assigned to this dose level, the infusion will be initiated at 0.139 g/h for the first 12 hours (approximately 3.33 g/24h), increased to 0.277 g/h (approximately 6.65 g/24h) for the next 12 hours, and then increased to 0.416 g/h (approximately 10 g/24h or 20.8 mL/h) for the remainder of the treatment period.
 
The dosing level for Dose Level 4 is defined follows:
 
Dose Level 4:
 
For patients in Cohorts 1 and 2, the infusion of OCR-002 will be initiated at 20g/24hr for a maximum time of 120 hours (approximately .83g/h), provided the dose level is well tolerated with no noteworthy side effects.
 
Initiation of each higher dose for patients in Dose Levels 1 through 3 and continuation of study drug administration for patients in Dose Level 4 will occur only if there are no treatment emergent SAEs of CTCAE Grade 4 or higher that are not attributed to acute liver failure in the opinion of the investigator.
 
In all dose levels, if 1 out of the 3 patients within a dose group experiences a treatment emergent SAE of CTCAE Grade 3 that is not attributed to acute liver failure, then an additional patient will be enrolled into that specific dose group. Within a given dose level, if 2 or more patients experience a treatment emergent SAE of CTCAE Grade 3 that is not attributed to acute liver failure in the opinion of the investigator, then dose escalation (Dose Levels 1 through 3) or continuation of study drug administration (Dose Level 4) will stop. Dose escalation or continuous administration also will stop if 1 patient experiences a Grade 4 or higher SAE that is not attributed to acute liver failure in the opinion of the investigator. Otherwise, dose escalation and continuous study drug administration will continue to the maximum tolerated dose and the remaining enrolled patients will be treated at this dose. Further details of dose

----------------------------	---

Treatment Continued	
escalation are provided in the protocol.
 
The Study Treatment listed below occurs in consecutive order. After the completion of each Dose Level (for each Cohort) the SRC will receive a safety report.
 
The first 3 enrolled patients will have minimal renal dysfunction (Cohort 1) and will be treated at Dose Level 1 for up to five days.
 
If patient safety is confirmed, the next 3 enrolled patients will also have minimal renal dysfunction (Cohort 1) and will receive an initial infusion of study drug at 0.139 g/h for the first 12 hours. The dose will be titrated, provided the previous dose level is well-tolerated with no noteworthy side effects, to the maximum dose in Dose Level 2 for 108 hours.
 
Study enrollment will be paused while the SRC reviews the safety and PK data for the first six evaluable Cohort 1 patients. If patient safety is confirmed, the next 3 Cohort 1 patients (minimal renal dysfunction) will receive an initial infusion of study drug at Dose Level 3 for 12 hours. The dose will be titrated to the maximum dose in Dose Level 3, provided previous dose levels are well-tolerated with no noteworthy side effects, to the maximum dose in Dose Level 3 for 96 hours.
 
In parallel with the enrollment of Cohort 1 patients (minimal renal function) at Dose Level 3, three patients with compromised renal function (Cohort 2) will be enrolled and treated at Dose Level 1 for five days.
 
If patient safety is confirmed, three Cohort 2 patients (compromised renal function) may be enrolled and will be treated with an initial infusion at Dose Level 2 for 12 hours. The dose will be titrated, provided the previous dose level is well-tolerated with no noteworthy side effects, to the maximum dose in Dose Level 2 for 108 hours.
 
The SRC will review the safety and PK data for Cohort 1 (minimal renal dysfunction) patients who received the study drug at Dose Level 3 and for Cohort 2 patients (compromised renal function) who received the study drug at Dose Levels 1 and 2 prior to enrolling Cohort 2 patients into Dose Level 3.
 
Once patient safety has been confirmed by the SRC for Cohort 1 patients in Dose Level 3, patients in Cohort 1 can begin to enroll into Dose Level 4 (20g/24hr) and will receive the full dose level from initiation of infusion for a maximum time of 120 hours, provided this dose is well tolerated with no noteworthy side effects. Once safety has been confirmed by the SRC for Cohort 2 patients in Dose Level 3, patients in Cohort 2 can begin to enroll into Dose Level 4 (20g/24hr) and will receive the full dose level from initiation of infusion for a maximum time of 120 hours, provided this is well tolerated with no noteworthy side effects. If a patient experiences CTCAE grade 1 or 2 adverse reactions or intolerance to the assigned dose, the investigator may choose to titrate to a lower dose in 5 gram increments and closely monitor the patient. The infusion rate and dose may be discontinued if the patient experiences CTCAE grade 3 or higher, or any time at the investigator's discretion.

Study	Up to 36 evaluable male and female patients aged 18 to 65 years (have not reached

Population	their 66th birthday) with acute liver failure or severe acute liver injury will participate.
Key Inclusion Criteria	
 1. Men and women, ages 18-65 (have not reached their 66th birthday). 2. Acute liver failure, defined as the development of coagulopathy (International normalized ratio [INR] ≥ 1.5) with encephalopathy in a patient with no prior history of liver disease with onset of symptoms within 28 days of the inciting event. Patients may have either a history of acetaminophen overdose (defined as >4 g/day within 7 days of presentation) and/or detectable acetaminophen levels in the serum, with a pattern of liver function tests typical for acetaminophen toxicity (bilirubin < 10 mg/dL and alanine aminotransferase (ALT) ≥ 1000 IU/L), or a diagnosis of hepatitis A, hepatitis B, drug-induced liver injury, autoimmune hepatitis or indeterminate cause based on standard criteria; refer to Section 6.2.1 for the definitions of standard criteria for these diagnoses. 3. ALI patients may also be enrolled (those meeting the above criteria plus coagulopathy (INR ≥ 2.0) and no evidence of encephalopathy and may provide consent themselves. 4. Written informed consent from the patient or patient's legally authorized representative or family member as defined in 21CFR50.3(m)--if he/she has evidence of encephalopathy (ALF). 5. Ammonia level ≥ 60 μmol/L at baseline (within 8 hrs prior to infusion start time). 6. Serum creatinine levels as follows: 
 a. Cohort 1: Creatinine ≤ 1.5 mg/dL; and b. Cohort 2: Creatinine >1.5 mg/dL and < 10 mg/dL. 7. Mean arterial pressure of >65 mmHg.
Key Exclusion Criteria	
 1. History of chronic liver disease 2. Signs of overt cerebral herniation, or uncontrolled intracranial hypertension by ICP monitoring (if applicable) 3. Evidence of Wilson's disease, alcoholic hepatitis, biliary obstruction, ischemic hepatitis, severe acute renal tubular necrosis (ATN) due to shock, or any patient with ongoing hypotension 4. Significant gastrointestinal bleeding (coffee grounds per ng tube and/or melena) 5. Hemodynamic instability, defined by a mean arterial pressure of <65 mmHg 6. Cardiopulmonary complications such as pulmonary edema, aspiration pneumonia, heart failure 7. QT interval of >500 msec at baseline ECG 8. Pregnancy 9. History of malignancy that has not been cured or any cancer in remission for less than 1 year. Non-melanoma skin cancers do not preclude participation in the trial. 10. Concomitant administration of drugs known to interfere with renal excretion of phenylacetylglutamine or those medications that may induce hyperammonemia

Key Exclusion Criteria Continued	
such as haloperidol, valproic acid and systemic corticosteroids (prohibited during the study). Alternative ammonia modifying agents such as lactulose and rifaximin are not considered standard of care and are prohibited during the study period.
 
11. Any other health condition that would preclude participation in the study in the judgment of the site principal investigator.

Safety Evaluations	
Safety assessments will be performed at:
 
 - Specified time points during the infusion periods (0 to up to 120 h) - At the Completion of the Last Infusion and 24 hours Following the Completion of the Last Infusion - End of study 
During the infusion period, at the Completion of the Last Infusion and 24 hours Following the Completion of the Last Infusion, daily safety assessments will include: abbreviated physical examinations, vital signs (blood pressure, pulse rate, respiration rate, and body temperature), clinical laboratory tests (hematology and serum chemistry), 12-lead ECGs, and reported and observed adverse events.
 
At the Day 30 follow up visit, safety assessments (physical, vitals, hematology/chemistry) including serious adverse events data will be collected.

Exploratory Efficacy Evaluations	
Ammonia concentrations will be collected during the infusion period, at the Completion of the Last Infusion, 24 hours Following the Completion of the Last Infusion and at the Day 30 post treatment period. Neurological assessments measured by the Glasgow Coma Scale and the West Haven Criteria will be done every 12 or 24 hours during the entire infusion period. Orientation log (O- log) assessment will also be undertaken in all patients at these time points.

Concomitant Medications and Therapy	
All patients will receive or have received, intravenous N-acetylcysteine (NAC) for acetaminophen toxicity.
 
Third generation cephalosporins, hypertonic saline and/or mannitol are permitted.
 
The use of hypothermia therapy is prohibited during the study.

Safety Analysis	
All adverse events will be summarized by body system, preferred MedDRA term and cohort. Data listings and summaries of severity, relation to treatment and expectedness will be provided by cohort.

Statistical Considerations	
This study is not powered to determine statistical significance. Descriptive statistics will be used to evaluate safety, exploratory efficacy data, PK and PD.

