3.3.2 Rationale for Dose Selection

Ocera Therapeutics, Inc. (Durham, NC) has conducted two clinical trials evaluating safety, tolerability and pharmacokinetics in healthy volunteers (n=48) and stable cirrhotic patients (n=43).

Clinical study OCR-002 HE201 was designed as a randomized, placebo-controlled, dose-ranging study, evaluating doses (i.v. infusion) of 1, 3, 10, 20 and 30g given over 4h, and 30, 40 and 60g given over 24h. Following a single ascending dose phase, a multiple ascending dose phase (5d of consecutive administration) for doses of 1, 3, 10 and 20g given over 4h was assessed. The key findings in this study included:

There were no deaths, SAE or AE discontinuations in the study.

A dose related increase in the incidence and severity of adverse events was observed.

Commonly occurring adverse events that appeared to be related to dose included dizziness, somnolence, headache, nausea/vomiting and tinnitus.

There was no evidence to suggest that AEs increased or new AEs occur with multiple dosing.

With respect to blood pressure, there were no apparent trends from placebo with respect to mean changes from baseline; however at dose levels $\geq 20\text{g}/4\text{h}$, several patients experienced clinically significant orthostatic hypotension.

There appeared to be a dose and exposure related increase in mean heart rate starting at a dose level of $10\text{g}/4\text{h}$ and higher. These effects also persisted for longer periods in the higher dose groups.

20g administered over 4 h was the maximum tolerated dose (MTD), however, doses of $10\text{g}/4\text{h}$ and below were well tolerated.

24h Holter monitor recording identified a dose-related increase in heart rate accompanied by modest effects on ventricular repolarization as measured by QT. These effects should be interpreted with caution in light of the small sample size and higher heart rates observed in this study.

There were no clinically significant abnormal laboratory parameters and no patient had any clinically significant changes in physical examination findings or mean

change in body weight between baseline and follow up.

Doses higher than 10g/4h are associated with adverse effects that may be rate and C_{max} related and are likely associated with the non-linear pharmacokinetic profile of phenylacetate above 10 g.

A slower infusion rate (24hr-infusion) avoids C_{max} related adverse effects while providing similar excretion of PAGN.

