5.2 Continuous Infusion Rate Adjustments

OCR-002 will be infused intravenously (IV) for up to 5 days (0 to 120 h). The Dosing regimen for Cohorts 1 and 2 is as follows:

Dose Level 1: Patients will receive the initial infusion of study drug at 0.139 g/h for the first 12 h (approximately 3.33 g/24h) and maintained at this rate for up to 120h.

Dose Level 2: Patients will receive an initial infusion of study drug at a dose of 0.139 g/h for the first 12 hours (approximately 3.33 g/24h). The dose will be increased to 0.277 g/h for the next 108h (approximately 6.65 g/24h), and maintained at this rate for the remaining treatment period, provided the previous dose level is well- tolerated with no noteworthy side effects and no safety signals are apparent.

Dose Level 3: Patients will receive an initial infusion of study drug at a dose of 0.139 g/h for the first 12 h (approximately 3.33 g/24h). The dose will be increased to 0.277 g/h for the next 12 hours, and then increased to 0.416 g/h (approximately 10 g/24h) and maintained at this rate

for the remaining treatment period, provided previous dose levels are well-tolerated with no noteworthy side effects and no safety signals are apparent.

Dose Level 4: Patients will receive an infusion of study drug at a dose of 20g/24h from initiation of infusion for a maximum time of 120 hours, provided the dose level is well tolerated with no noteworthy side effects and no safety signals are apparent.

If a patient experiences CTCAE grade 1 or 2 adverse reactions or intolerance to the assigned dose, the investigator may choose to titrate to a lower dose in 5g increments and closely monitor the patient. The infusion rate and dose may be discontinued if the patient experiences CTCAE grade 3 or higher, or any time at the investigator's discretion. (See Section 9.7 of the protocol for details on safety review, dose escalation and trial stopping criteria.)

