6.3.4 Discontinuation of Study Treatment

An Investigator may discontinue a patient's treatment at any time to protect the patient's safety. Reasons that patients may have treatment discontinued include, but are not limited to the following:

- Prolongation of Qt/Qt_c interval of >60 msec over baseline or a Qt/Qt_c interval above 500 msec;
- Evidence of torsades de pointe phenomenon;
- Grade 3 or higher CTCAE toxicity not attributed to acute liver failure in the opinion of the investigator;
- Neutropenia with absolute neutrophil count <500/cumm or platelet count <20,000/cumm, or an increase in serum Cr to a value of >10mg/dL;
- Liver transplantation during the study treatment;
- Withdrawal of informed consent by the patient or patient's legally authorized representative or family member;
- In the case of interruption of infusion for any reason, the study drug will not be restarted if more than 2 hours has elapsed;
- Evidence of shock; and
- Evidence of kidney injury related to study drug will invoke consideration of discontinuation of the study drug.

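### At the same event counts, the synopsis stops escalation or Dose Level 4 drug, while section 9.7.1 counts only unexpected SAEs and orders only a recruitment pause and review

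*Combined protocol and SAP*

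**What the plan says.** **Synopsis, Treatment.** Each higher dose at Levels 1 to 3 is conditional, and the same sentence says of Level 4: "continuation of study drug administration for patients in Dose Level 4 will occur only if there are no treatment emergent SAEs of CTCAE Grade 4". The condition takes in higher grades too, and concerns events that the investigator does not attribute to ALF. Two action sentences follow. If two or more patients at a dose level have a Grade 3 SAE not attributed to ALF, "then dose escalation (Dose Levels 1 through 3) or continuation of study drug administration (Dose Level 4) will stop". For the higher grade, "Dose escalation or continuous administration also will stop if 1 patient experiences a Grade 4 or higher SAE", again if not attributed to ALF. Neither sentence mentions expectedness. The synopsis also has an optional rule for the individual patient: "The infusion rate and dose may be discontinued if the patient experiences CTCAE grade 3 or higher".

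**Section 5.2.** It repeats that optional sentence. Level 4 dosing is given "provided the dose level is well tolerated with no noteworthy side effects and no safety signals are apparent", and similar conditions apply to the within-patient steps at Levels 2 and 3. It then refers onward: "See Section 9.7 of the protocol for details on safety review, dose escalation and trial stopping criteria".

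**Section 6.3.4.** The list opens with "Reasons that patients may have treatment discontinued include, but are not limited to the following". Toxicity of Grade 3 or above not attributed to ALF is one of the listed reasons.

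**Section 9.7.1.** The counts match the synopsis (two or more patients at Grade 3, one patient at Grade 4 or higher), but the events must be unexpected SAEs. The consequence is that recruitment is suspended, the Medical Safety Monitor (MSM) reviews the data, and the Safety Review Committee (SRC) recommends termination or continuation.

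**Sections 9.1.2 and 9.1.6.** Section 9.1.2 names nine events as expected with the drug: tachycardia, hypotension, dizziness, nausea, vomiting, headache, chills, somnolence and restlessness. Section 9.1.6 defines unexpected events.

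**The concern.** Safety and tolerability is the primary objective, and these rules are the main formal protection for patients. Level 4 starts without titration at 20 g/24h, twice the Level 3 maximum. A site that follows the pointer in 5.2 reaches 9.7.1. There it finds a narrower trigger and an action aimed at recruitment, with nothing about patients on infusion. The restriction to unexpected events also bears hardest on the drug's own known reactions, which a tolerability study most needs to count. The same event could therefore stop drug under one part of the protocol and trigger nothing under another.

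**Working it through.** The plan gives no figure to reproduce. Section 11.3 reports no formal sample size calculation, and no operating characteristics are stated for the stopping rule. The check is a comparison of texts.

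**Step 1. The two rules side by side.**

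| Element | Synopsis | Section 9.7.1 |
|---|---|---|
| Grade 3 count | 2 or more patients in a dose level | 2 or more patients in a dose level |
| Grade 4+ count | 1 patient | 1 patient |
| Expectedness | Not a condition | Unexpected SAEs only |
| Attribution | Not due to ALF, both grades, investigator's opinion | Not due to ALF, attached to Grade 3; reach to Grade 4+ unclear; no assessor named |
| Action | Escalation stops (Levels 1–3) or drug administration stops (Level 4) | Recruitment suspended; MSM review; SRC recommendation |
| Running infusions | Level 4 administration stops | Not addressed |

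The counts agree. The set of events and the action do not.

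**Step 2. Example events put through both rules.**

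- *Grade 4 SAE, not due to ALF, not listed for the drug.* Synopsis: escalation or Level 4 drug stops. Section 9.7.1: triggered, but it orders only the recruitment pause and review.
- *Grade 4 hypotension SAE, not due to ALF.* Synopsis: triggered. Section 9.7.1: undetermined. The conditions in 9.1.2 are joined by *or*, so listing in the Investigator's Brochure is enough to make the event expected. Under 9.1.6 it is unexpected if the observed severity is not listed. Both definitions can apply at once.
- *Grade 3 tachycardia SAEs, not due to ALF, in two patients at one level.* Same result as for hypotension.
- *Grade 4 event due to ALF.* Synopsis: not triggered. Section 9.7.1: if the event is classed as unexpected, the sentence can be read to include it, because the ALF qualifier sits with the Grade 3 limb.

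**Step 3. The individual-patient sections.** The optional wording of 5.2 is also in the synopsis, so it is not a general contradiction between synopsis and body. A general *may* at Grade 3 or above can stand beside a specific *will* for a narrower event. The clash is direct in one case: a Level 4 patient with a Grade 4 or higher SAE not attributed to ALF, where the synopsis requires a stop and 5.2 and 6.3.4 permit one.

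**Step 4. Scope.**

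- Level 4 is planned for up to 12 of 36 evaluable patients (section 3.3.2): 12/36 = 33%.
- Level 4 against the Level 3 maximum: 20/10 = 2.
- Terms listed as expected with the drug: 9.
- Section 3.3.2 reports that at 20 g/4h and above "several patients experienced clinically significant orthostatic hypotension". That rate is 20/4 = 5 g/h; Level 4 is 20/24 = 0.83 g/h; the ratio is 6. This shows that hypotension is a known effect of the drug. It does not predict its frequency at Level 4.

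**The case against.** **The rules work at different levels.** Section 9.7.1 concerns the trial and its recruitment; the synopsis concerns dosing. Both can apply to one event, and 9.7.1 does not cancel the synopsis, which is part of the protocol. This is fair as far as it goes. It does not explain the different set of events, and 5.2 names 9.7 as the place for dose escalation and stopping criteria.

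**Section 5.2 already protects patients.** Its conditions on tolerability and safety signals name no grade, so they can be stricter than a Grade 4 threshold. An investigator who sees a life-threatening SAE not due to ALF would normally stop that infusion. Moves between levels also need SRC review, and 6.3.4 lists shock. This largely stands. It reduces the gap, most of all at Levels 1 to 3, but gives no rule for the dose level as a whole.

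**Severe forms of listed reactions may still count as unexpected.** Section 9.1.2 gives the nine terms without severity, and the Investigator's Brochure is not available here. That is why the result is stated as unclear and not as a definite miss. The earlier volunteer study reported no SAEs, gave up to 60 g over 24 h, and found that slower infusion avoids effects related to peak concentration.

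**Stronger readings that a reader might infer.**

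- *That the body makes stopping optional throughout.* The synopsis shares the optional sentence.
- *That a patient could stay on drug for 24 + 72 = 96 h before an MSM opinion.* The sum bounds nothing. The 24 h reporting limit runs from first knowledge, forwarding to the MSM has no stated limit, and the 72 h opinion concerns seriousness, expectedness and relatedness, in a process that leads to expedited reporting. It does not decide whether drug stops.
- *That all other Level 4 infusions must be held pending review.* The synopsis stops administration at Level 4 but describes no such hold.

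**Conclusion.** The inconsistency is real and is limited to the following. At identical counts, the synopsis and 9.7.1 differ in which SAEs qualify and in what then happens. The nine listed reactions are where the triggers may diverge, and 9.1.2 and 9.1.6 do not settle the matter when the observed severity is not listed. Sections 5.2 and 6.3.4 conflict directly with the synopsis only for a Level 4 patient with a qualifying Grade 4 or higher SAE, and the conditions in 5.2 narrow that gap without closing it.

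No event probability is claimed, because the documents give no rate of qualifying SAEs, and no limit on excess exposure time can be derived. The conclusion assumes that the SRC charter, which is not in the documents, does not already reconcile the two rules. Even if it did, site staff who work from the protocol would still read two versions.

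**What to change.** **In 9.7.1:**

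1. Delete *unexpected* from the trigger.
2. Apply the synopsis's qualifier (the investigator judges the event not due to ALF) to both the Grade 3 and the Grade 4 or higher limb.
3. Beside the recruitment suspension and the MSM and SRC review, add the synopsis action: escalation stops at Levels 1 to 3, and study drug administration stops at Level 4.

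**In 5.2 and 6.3.4:** state that the optional discontinuation wording is subject to this rule for Level 4.

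Do not add a mandatory infusion stop for individual patients at Levels 1 to 3. The synopsis stops only escalation there, so that would be a new rule.

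**Cost.** An amendment to the wording and a notice to sites, with no new committee or procedure. Recruitment pauses may become more frequent because listed drug reactions would count. Level 4 patients stopped before 72 h would not be evaluable, and so would fall outside the per-protocol population that section 11.4 makes primary; some might need replacing.
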